The HepQuant SHUNT Liver Diagnostic Kit contains one 20 mL vial of 25% human serum albumin, one 30 mL vial containing 10 mL of 40 mg cholate labeled with 4 deuterium atoms (d4-cholate) in sodium bicarbonate solution for oral dosing, one 10 mL val containing 5.5 mL of 22 mg cholate labeled with carbon-13 (13C-cholate) in sodium bicarbonate solution for intravenous injection (5.0 mL, 20 mg is injected),), a 3-way stopcock, pipettes, transfer tubes, instructions for use, labels, and materials for mailing serum to HepQuant's reference laboratory. Cholates and albumin are natural endogenous compounds of the human body. The labels, d4 and 13C, are cold stable labels and are NOT RADIOACTIVE. Deuterium and carbon-13 are naturally abundant in the human body – deuterium represents approximately 0.0156% of all hydrogen atoms and carbon-13 represents 1.1% of all carbon atoms. There is no significant increase in the body's pools of deuterium or carbon-13 from administration of doses of d4- and 13C-cholates used in the HepQuant SHUNT test.

The HepQuant SHUNT test measures liver function (cholate uptake), and physiology (hepatic and portal inflows and portal-systemic shunting) from simultaneous clearance of both the orally and intravenously administered d4and 13C-cholates. Six timed blood samples (3 mL each) are obtained at 0, 5±1, 20±2, 45±5, 60±5, and 90±5 minutes. Concentrations of d4- and 13C-cholate are measured by LC/MS, clearances defined, and hepatic filtration rates, SHUNT, STAT, and DSI calculated. DSI has a range from 0 to 50 based upon results from over 1600 tests in over 700 persons.

Study's Duration:

18-24 months

[figure not shown]
Participant's Duration:

[figure not shown]
From 3 to 100 days

Sample Size and Power:

The study will enroll no more than 420 subjects, to provide 80% probability (power) that the upper limit of the 95% CI for the observed NLR_0 is <0.52 for the DSI cutoff of 18.3 in identifying subjects unlikely to have large esophageal varices.

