9.4.2 ANALYSIS OF THE PRIMARY EFFICACY ENDPOINT(S)

[figure not shown]
Primary efficacy endpoint (DSI \leq18.3 "Rules Out" Large Esophageal Varices): The independent variable is DSI and the dependent variable is the presence/absence of large esophageal varices diagnosed by EGD within 42 days of the HepQuant SHUNT test. The sample size evaluation of section 9.2.1 is based on the large-sample variance of **Table 9** equation E. This equation cannot be used for data analysis if sensitivity is close to 1.0 (Marril, et al [118]). The following methods will be used to evaluate whether the trial results satisfy the performance goals for NLR and sensitivity:

Rule out NLR > 0.52: This objective will be satisfied if the upper limit of the confidence interval for NLR is smaller than 0.52. The score-based confidence interval that is derived by inverting the score test (see Marril, et al. [118]) will be used to calculate the NLR confidence interval. The confidence level will be chosen to assure an overall one-sided type-I error rate of 0.025 as described in section 9.5.1.

Sensitivity >= 0.85: This objective will be satisfied if the observed sensitivity is larger than 0.85. The corresponding 95% confidence interval will also be reported and will be calculated using the exact binomial distribution.

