9.5 Summary and Implications of Validating the Primary Endpoint

We anticipate test performance to be similar between the HALT-C Training dataset and the CLD Validation datasets. In the HALT-C Training dataset with prevalence of large varices of 10%, DSI \leq 18.3 yielded sensitivity 95%, specificity 54%, NLR 0.0926, NPV 99%, and FNR 1%. Therefore, we expect the NLR and upper limit of the 95% CI for NLR to meet the validation criteria: upper limit of 95% CI <NLR₀, or <0.52, and observed sensitivity > 0.85. There are several clinical implications of this validation.

DSI ≤18.3 improves the diagnostic performance to "Rule Out" Large Varices. The high sensitivity and moderate specificity of DSI ≤18.3, compared to the lower sensitivity and specificity of publication of LSM plus platelet count, suggest that the DSI cutoff might perform well in identifying the cases free of large varices who might avoid screening EGD. The HALT-C Training dataset results suggested that up to 50% of screening EGDs might be avoided. In contrast, the data with LSM plus platelet count suggested that only 20% of screening EGDs might be avoided.

DSI \leq **18.3 lowers the FNR for Large Varices.** The pre-test odds of large esophageal varices is given by $[\pi/(1-\pi)]$, where π is prevalence of large varices. For prevalence of 10%, the pre-test odds (0.1/0.9) for large esophageal varices is 0.11. The post-test odds of large esophageal varices is given by: NLR x $[\pi/(1-\pi)]$. For NLR of 0.0926, the post-test odds of large esophageal varices for DSI \leq 18.3 was: 0.0926 x (0.1/0.9) = 0.0102, or a pre- to post-test reduction in odds for large varices of 11.0 – a highly significant reduction based on DSI.

In contrast, for an average NLR of 0.27 and prevalence of 11% (pre-test odds (0.11/0.89) = 0.12) from the 10 published studies of LSM plus platelet count, the post-test odds of large esophageal varices was 0.27 x (0.11/0.89) = 0.033, or odds ratio of 3.6. This comparison suggests that DSI has better diagnostic performance.

Applying these results for DSI to the CLD Validation dataset where the prevalence of large esophageal varices is projected to be 20% yields a post-test odds for large varices of $0.09 \times (0.2/0.8) = 0.0225$. In comparison, LSM plus platelets would yield a post-test odds for large varices of $0.27 \times (0.2/0.8) = 0.0675$. The data suggests that DSI has a lower FNR than LSM plus platelet count over the prevalence range of 10 to 20% for large varices.

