9.5.1 PLANNED INTERIM ANALYSIS

One interim analysis is planned after the analysis data sets contain complete results (DSI measurements and EGD examination results) on at least 250 participants. The objective of the interim analysis will be to evaluate whether the interim results would allow the trial to be stopped for either efficacy or futility; i.e., because the performance goals for DSI < 18.3 as a test for ruling out large varices has been satisfied (efficacy) or because it is futile to continue because sensitivity is too low and NLR is too large.

Process for preparing and reviewing interim analysis: The trial database is maintained by an independent CRO. Trial investigators do not have access to DSI results, and the Sponsor does not have access to EGD findings. The interim analysis will therefore be performed by a statistician independent from both the sponsor and the CRO. The results of the interim analysis will be reviewed and interpreted by the independent biostatistician using the interim decision criteria to make a recommendation to HepQuant to either continue or stop the trial based on the interim results. If the determination is made to continue the trial, no further analyses will be conducted until the full recruitment is reached, and no blinded information will be provided to the sponsor, the CRO, or any investigator. If the determination is made to stop the trial, analysis of all endpoints will be performed on the interim data (N=250) according to the trial SAP.

Decision criteria for the interim analysis: The interim decision criteria are based on standard methods for group sequential clinical trial design as published by Emerson, et. al. [117] as implemented in the software package RCTdesign. With complete results on 250 subjects the independent unblinded statistician will convey one of three conclusions based on the results of the data analysis:

- i. The efficacy decision criteria have been satisfied: This conclusion is reached if:
 - a. The upper limit of the 97.64% score-based confidence interval for NLR is less than 0.52, and
 - b. the observed sensitivity greater than or equal to 0.85.
- ii. *The futility decision criteria have been satisfied:* This conclusion is reached if:
 - a. The upper limit of the 51.41% score-based confidence interval for NLR is larger than 0.52, and
 - b. the observed sensitivity less than 0.85.
- iii. Neither the efficacy nor the futility decision criteria have been satisfied.

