In the case of the second conclusion, i.e., futility, the trial will be stopped; the assessment of futility represents a binding assessment.

In the case of the third conclusion, the trial will continue to the full sample of 400 subjects with complete data. If the study is not stopped early, then the full-sample (N=400) analysis will reach an efficacy conclusion if the upper limit of the 96.07% confidence interval is smaller than 0.52 and the observed sensitivity is greater than or equal to 0.85.

If the efficacy or futility decision criteria are satisfied, then HepQuant will request the analysis data set and analysis report from the independent statistician. HepQuant will reproduce the analysis from the independent statistician and initiate the trial termination processes. If neither the efficacy nor futility criteria are satisfied, then HepQuant will remain blinded and will not receive the results of the interim analysis. The independent statistician will archive the analysis and the interim analysis data set for reference upon trial completion.

The power and type I error rate using the above interim decision criteria have been evaluated in a simulation study as described in section 9.4.2 and summarized in **Table 12**. The simulation study also calculates the probability that the trial will satisfy the interim decision criteria. **Table 13** summarizes the chance of satisfying the interim efficacy and futility decision criteria as a function of the true NLR when true sensitivity is 90%.

	Decision	s at N=250	Decisions	at N=400	Total power
NLR	Futility	Efficacy	Futilty	Efficacy	for Efficacy
		20% prevale	nce of large v	arices	
0.52	0.744	0.004	0.241	0.011	0.015
0.40	0.521	0.022	0.403	0.055	0.077
0.30	0.220	0.124	0.433	0.223	0.348
0.20	0.118	0.652	0.027	0.203	0.855
0.15	0.120	0.880	0.000	0.001	0.880
		25% prevale	25% prevalence of large varices		
0.52	0.747	0.005	0.236	0.012	0.017
0.40	0.484	0.032	0.416	0.069	0.100
0.30	0.184	0.166	0.394	0.256	0.422
0.20	0.100	0.760	0.013	0.128	0.888
0.15	0.098	0.902	0.000	0.000	0.902

Table 13: Probability of reaching the futility and efficacy decisions at the interim (N=250) and full sample(N=400) analyses. Probabilities from simulations for the indicated NLR when sensitivity = 0.90.

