The interim analysis improves the efficiency of the trial by allowing early stopping for efficacy if the DSI test has NLR=0.15 (88% chance of stopping at the interim analysis with 20% large varices) or for futility under the null hypothesis of NLR=0.52 (77% chance of stopping at the interim analysis with 20% prevalence of large varices).

Statistical analyses and reporting of results: Although the confidence levels for NLR in the interim decision criteria have been adjusted to maintain the one-sided level 0.025 type I error rate, study results will be reported using 95% confidence intervals as described in section 9.4.1. Exact methods for proportions and the score-based confidence intervals for ratios of proportions will be used for 95% confidence intervals when reporting results for NLR, sensitivity, and other measures of diagnostic accuracy.

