The NLR performance goals for the STAT cutoff applied to the CLD Validation dataset are identical to the goals explained above for DSI: that the upper limit of the 95% Confidence Interval for NLR rules out NLR > 0.52. The sample size considerations with DSI for the primary efficacy endpoint and secondary efficacy endpoint 1 are also applicable STAT – the same limits for sensitivity and specificity. We will include age, gender, race, and ethnicity in multi-variable logistic regression of the association of STAT with large esophageal varices.

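### Success on NLR is decided at 97.64% or 96.07% confidence, but the plan reports only an unadjusted 95% interval and restates the criterion at 95% in section 9.5: a reporting and consistency defect, not a loss of type I error control

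*Combined protocol and SAP*

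**What the plan says.** **Decision level.** Section 9.4.2 says of the NLR interval: "The confidence level will be chosen to assure an overall one-sided type-I error rate of 0.025 as described in section 9.5.1". Section 9.5.1 supplies the levels. At the interim: "The upper limit of the 97.64% score-based confidence interval for NLR is less than 0.52, and" the observed sensitivity must reach 0.85. At the end, efficacy requires that "the upper limit of the 96.07% confidence interval is smaller than 0.52 and the observed sensitivity is greater than or equal to 0.85". The endpoint paragraph of the synopsis (1.1) and the table in section 3 also say that the level is adjusted as in 9.5.1.

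**Reporting level.** The closing paragraph of 9.5.1 acknowledges the adjustment and then states that "study results will be reported using 95% confidence intervals as described in section 9.4.1", using score intervals for ratios and exact intervals for proportions. If the trial stops early, all endpoints are analysed on the N=250 data. The plan does not ask for the decision-level interval to be shown, and it contains no estimate or interval corrected for the sequential design.

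**Restatements at 95%.** Section 9.5 expects the trial "to meet the validation criteria: upper limit of 95% CI" below 0.52, with observed sensitivity above 0.85. Section 9.6.2 says the STAT goals are the same as those for DSI, and words them so "that the upper limit of the 95% Confidence Interval for NLR rules out NLR > 0.52". The sample size paragraph of the synopsis, "that the upper limit of the 95% CI for the observed" NLR is below 0.52, and section 9.2.1 also use 95%, but these are power statements.

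**The concern.** The interval that readers see is not the interval that decides the trial. Every 96.07% interval is wider than the 95% interval from the same data. Some final results therefore fail the rule in 9.5.1 while the published interval excludes 0.52 and satisfies the criterion as worded in 9.5. A reader with only the report could not tell why the trial failed, and the protocol would support both answers.

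The second issue is estimation. By Table 13, stopping for efficacy at N=250 is the likeliest outcome if the test performs as hoped (0.652 at NLR 0.20 and 0.880 at NLR 0.15, with sensitivity 0.90 and 20% prevalence). Trials that cross an efficacy boundary do so partly by chance, so the unadjusted NLR among them is too favourable on average. Sections 3 and 9.6.2 foresee performance figures in a package insert, so the size of the estimate matters as well as pass or fail.

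**Working it through.** **Inputs.** Levels 97.64%, 96.07% and 51.41% (binding futility), looks at 250 and 400, and the sensitivity requirement of 0.85 come from 9.5.1. The null value of 0.52 and the score interval come from 9.4.2. The design point in 9.2.1 is sensitivity 0.90, specificity 0.50, NLR 0.20 and prevalence 20%. Critical values are z = Φ⁻¹(1 − (1 − level)/2): 2.264 for 97.64%, 2.061 for 96.07%, 0.697 for 51.41% and 1.960 for 95%.

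**1. The plan's own figures.**
- Table 9, equation E, at 80/320: V = 0.9/(0.1×80) + 0.5/(0.5×320) = 0.1125 + 0.003125 = 0.1156, SE = 0.340. Power = Φ(ln(0.52/0.20)/0.340 − 1.960) = 0.802 (Table 10: 0.80). Critical value = 0.52×exp(−1.960×0.340) = 0.267 (stated 0.27). So the 95% in 9.2.1 belongs to a fixed-design calculation. With z = 2.061 the same formula gives 0.773.
- Type I error by normal theory, correlation √(250/400) = 0.791: P(Z₁ > 2.264) + P(0.697 < Z₁ < 2.264, Z₂ > 2.061) = 0.0250, as stated.
- Simulation (400,000 trials per scenario, score test of the ratio at 0.52, number of large-varices cases binomial at 20%). Total power at sensitivity 0.90 and NLR 0.52/0.40/0.30/0.20/0.15 is 0.015/0.077/0.347/0.851/0.877, against 0.015/0.077/0.348/0.855/0.880 in Table 13. Table 13 is matched when failing either condition counts as interim futility. Section 9.5.1 as written requires both. That is a separate matter, so results below are given for both readings where they differ.
- Simulated type I error under the planned rule is 0.018, 0.015 and 0.007 at sensitivity 0.85, 0.90 and 0.95. It reaches 0.019 in runs at 25% prevalence or sensitivity 0.80. Table 12 shows at most 0.020 with the interim analysis.

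**2. A concrete conflict at N=400.** Take 80 cases with 8 missed, and 118 true negatives among 320. Sensitivity is 72/80 = 0.900, specificity 118/320 = 0.369, NLR = 0.100/0.369 = 0.271. The upper limit is the ratio r at which (x/V − r·t/M)/√(p̃₁(1−p̃₁)/V + r²p̃₂(1−p̃₂)/M) = −z, where x/V is the observed miss rate, t/M the observed specificity, and p̃₁ = r·p̃₂ are the restricted estimates. The limit is **0.511 at 95%** and **0.526 at 96.07%**. The trial fails, and its reported interval excludes 0.52.

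**3. How often.** Count trials reaching N=400 with observed sensitivity of at least 0.85 and a score statistic between 1.960 and 2.061 in favour of DSI:

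| Sensitivity | True NLR | Probability (either / both futility reading) |
|---|---|---|
| 0.90 | 0.20 (design point) | 0.40% / 0.65% |
| 0.90 | 0.30 | 4.1% / 4.3% |
| 0.95 | 0.20 | 5.1% / 5.2% |
| 0.95 | 0.0926 (training data) | 0.0% / 0.0% |

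Fixing the number of cases at exactly 20% gives 0.5% / 0.9% at the design point. The conflict cannot arise at the interim: an efficacy stop at 97.64% also excludes 0.52 at 95%, and if the 51.41% upper limit exceeds 0.52, so does the 95% limit.

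**4. Estimate after an efficacy stop at N=250** (sensitivity 0.90, 20% prevalence):

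| True NLR | Probability of efficacy stop | Mean unadjusted NLR given the stop | Mean over all trials (either / both) |
|---|---|---|---|
| 0.15 | 0.876 | 0.134 | 0.150 / 0.145 |
| 0.20 | 0.646 | 0.151 | 0.196 / 0.190 |
| 0.30 | 0.124 | 0.111 | 0.310 / 0.304 |

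Unconditional coverage of the unadjusted 95% interval is about 0.94 to 0.97 across the scenarios run.

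**The case against.** The strongest reply is that the rule is explicit and works. Section 9.5.1 fixes a level for each look, 9.4.2, section 3 and the synopsis endpoint paragraph defer to it, and type I error is held. The separation of decision and reporting is stated openly. At the sponsor's design point the conflict is a sub-1% event. The 5% case implies specificity 0.05/0.20 = 0.25, below the 0.28 that 9.4.2 calls acceptable, and the 4% case is one where power is only 0.348. The bias is conditional: over all trials the mean NLR and the coverage are close to target. STAT is exploratory. All of this stands, and it limits the weight of the point. It does not answer why 9.5 words the criterion differently from 9.5.1, or why the deciding interval is not to be reported.

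Two stronger readings are tempting and are not supported. First, a reader might infer that type I error exceeds 0.025. A 95% interval at both looks would give 0.038 by normal theory, and in simulation at 20% prevalence about 0.030, 0.025 and 0.014 at sensitivity 0.85, 0.90 and 0.95. But no section proposes that rule. Using 97.64% and then 95% gives 0.022, 0.019 and 0.012 in simulation (0.029 by normal theory). Second, a reader might infer that the synopsis states the criterion at 95%. Its endpoint paragraph says the level is adjusted, and the 95% sentence is a power statement that matches Table 10.

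**Conclusion.** The point holds as a reporting and consistency defect, worth correcting before analysis. The primary test is properly specified and controls one-sided type I error at the stated 0.025. What is missing is agreement between the deciding interval, the reported interval and the criterion in 9.5, together with an estimate that allows for early stopping. The conflict is confined to the final look: about 0.4% to 0.6% at the design point, under 1% there on every variant run, and about 4% to 5% for a test of intermediate performance. The larger practical effect is on the estimate after an efficacy stop: at sensitivity 0.90, a mean of 0.151 for a true 0.20 and 0.134 for a true 0.15.

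These figures assume 20% prevalence, exactly 250 and 400 evaluable subjects, and a score test of the ratio of proportions. A trial can also fail on sensitivity alone while its NLR interval excludes 0.52. That follows from the two-part goal and is not part of this point.

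**What to change.** - **Section 9.5.1, reporting paragraph:** report the primary NLR with the interval used for the decision (97.64% if stopped at the interim, 96.07% at the end). Add a group-sequential-adjusted estimate with its 95% interval, naming the method in advance. Keep the unadjusted 95% interval, labelled descriptive.
- **Section 9.5:** replace the 95% interval in the validation criterion with an interval at the level set in 9.5.1.
- **Section 9.6.2 (STAT):** either make the same change, or stop describing the goal as the same as the DSI goal.
- **Synopsis, sample size paragraph, and section 9.2.1:** mark these as fixed-design power calculations at 95%. Leave the synopsis endpoint paragraph unchanged.

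The cost is SAP wording and an extra table row, with no additional subjects or data. The headline interval becomes slightly wider and the adjusted NLR slightly less favourable.

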9.5.2 SAFETY ANALYSES

The known potential adverse events associated with the HepQuant SHUNT Test are primarily related to the indwelling intravenous catheter and the very rare risk for allergic reaction to human serum albumin. These are delineated in **Section 2.3.1**. AEs and SAEs are evaluated and recorded at Study Visits 2 and 3. While EGD findings are not reported, AEs and SAEs associated with the EGD itself are recorded. The Self-Reported Subject Tolerability survey is completed at Study Visits 2 and 3.

Safety events will be analyzed as summary statistics. AEs and SAEs will be coded according to the Medical Dictionary for Regulatory Activities (MedDRA). The incidence and frequency will be calculated by counting each AE once only for a given participant. Severity and frequency of AEs, and the relationship of AEs to study intervention will be presented by System Organ Class (SOC) and preferred term groupings. The following additional information will be reported about each AE: start date, stop date, severity, relationship, expectedness, outcome, and duration. Adverse events leading to premature discontinuation from the study intervention and serious treatment-emergent AEs will be presented in a table. The information will be consistent with the information contained within Section 8.3, Safety and Other Assessments.

9.5.2.1 ADVERSE EVENTS (AES)

Adverse events will be tabulated by subject by study visit – Visits 2, 3, and EGD-related.

9.5.2.2 SERIOUS ADVERSE EVENTS (SAES AND SUSARS)

Serious adverse events will be tabulated by subject by study visit – Visits 2, 3, and EGD-related.

9.6 BASELINE DESCRIPTIVE STATISTICS

Descriptive statistics will characterize:

- The total enrolled CLD population
- Subgroups of etiology of CLD
 - NASH and Cryptogenic cirrhosis
 - Viral (HCV and HBV)
 - o Alcohol
 - Cholestatic (PBC and PSC)
- Subgroups of severity of liver disease
 - $\circ~$ F3 Fibrosis stage with platelets <175,000 $\mu L^{\text{-1}}$
 - Compensated cirrhosis (Child-Pugh class A cirrhosis)
 - Decompensated Cirrhosis (Child-Pugh class B cirrhosis)

For descriptive statistics, categorical and continuous data will be presented as percentages, means with standard deviations, median, and range. For inferential tests, in comparing the characteristic of the two subgroups, p-value <0.05 (two-sided) and 95% confidence intervals will be required for statistical significance (Type I error).

